1.2. Schema

Figure 1: Schematic Overview of the Study

D = Day.

Note that the scale of the timelines is arbitrary for clarity purposes.

In Cohort 2, a blinded 24-hour (Day 2) postvaccination safety review of the sentinel group of 5 participants will be performed by the PI(s) and sponsor team members (Step 1). In the absence of any clinical safety concerns, an additional 15 participants will be enrolled (Step 2). After review of the 7-day (Day 8) postvaccination safety data of these 20 participants by the DRC, the remaining participants in the cohort will be enrolled (Step 3). Based on the review of all available safety data up to at least 7 days after vaccination of all participants in Cohort 2 by the DRC (dashed line), the sponsor may decide to not initiate enrollment of Cohort 3.

The enrollment of Cohort 3 will be conducted similarly to Cohort 2. Steps 1 and 2 will be performed with a sentinel group of 4 participants and with 12 participants, respectively. After review of the 7-day (Day 8) postvaccination safety data of these 16 participants by the DRC, the remaining participants in the cohort will be enrolled.

1.3. Schedule of Activities

1.3.1. Cohort 1

Clinic Visit #	1	2 ^a	3	4 ^a	5	6	Early Exit ^b
Visit Timing	Vac	Vac + 7 d	Vac + 14 d	Vac + 28 d	Vac + 84 d (3 m)	Vac + 26 wk (6 m)	
Visit Day(s)	1	8	15	29	85	183	
Visit Window		±2 d	-3 d/+7 d	±7 d	±14 d	±14 d	
Visit Type	SCREENING AND STUDY VACCINATION	Safety	Safety and Immunogenicity	Safety	Safety and Immunogenicity	Safety and Immunogenicity	Early Exit
Written informed consent ^c	●						
Inclusion/exclusion criteria	●						
Demographics	●						
Medical history/prestudy therapy ^d	●						
Physical examination ^e	●		●		●	●	●
Vital signs ^f	●		●		●	●	●
Randomization	●						
Participant diary distribution	●						
Contraindications to vaccination ^g	●						
Cellular immunity sample, mL	● 50		● 50		● 50	● 50	● 50
Humoral immunity sample, mL	● 10		● 10		● 10	● 10	● 10
Nasosorption sample	●		●		●	●	●
Vaccination	●						
30-minute postvaccination observation ^h	●						
Solicited AE recording ⁱ	- - Continuous - -						●
Unsolicited AE recording ^j	- - - Continuous - - -						●
SAE recording ^k	- - - Continuous - - -						●
Concomitant therapy ^l	- - - Continuous - - -						●
Participant diary review of solicited AEs by study-site personnel ^m		●					
Blood draw volumes							
Approximate daily blood draw, mL	60	-	60	-	60	60	60
Approximate cumulative study blood draw, mL	60	60	120	120	180	240	-

d = day; m = month; Vac = vaccination; wk = week.

❶ prevaccination; ❷ pre- and postvaccination; ❸ if the early exit visit is within 8 days after vaccination; ❹ blood samples for immunogenicity will only be taken if the early exit visit is at least 14 days after the previous immunogenicity blood draw; ❺ if the early exit visit is within 7 days after vaccination; ❻ if the early exit visit is within 28 days after vaccination; ❻ at the discretion of the investigator (based on health status of the participant).

- a. Can be electronic (eg, e-mail, text messages) or by phone.
- b. An early exit visit will be conducted for those participants who are unable to continue participation in the study and withdraw from the study before Day 183, but who do not withdraw consent. Participants who wish to withdraw consent from participation in the study will be offered an early exit visit (prior to formal withdrawal of consent).
- c. Signing of the ICF should be done before any study-related activity.
- d. Prestudy therapies administered up to 30 days before vaccination must be recorded.
- e. A physical examination (including height and body weight) will be carried out at screening. At all other visits, an abbreviated, symptom-directed physical examination will be performed if deemed necessary by the investigator.
- f. Systolic and diastolic blood pressure (supine) and heart and respiratory rate measurements should be preceded by at least 5 minutes of rest in a quiet setting without distractions (eg, television, cell phones). Vital signs measurements should be taken before nasal sampling and blood draws, if applicable.
- g. Investigator must check for acute illness or body temperature of $\geq 38.0^{\circ}\text{C}$ ($\geq 100.4^{\circ}\text{F}$) at the time of vaccination. In such cases, the participant may be vaccinated up to, and no later than, 10 days after the scheduled vaccination, or be withdrawn from vaccination at the discretion of the investigator.
- h. After vaccination, participants will be closely observed for a minimum of 30 minutes to monitor for the development of any acute reactions and solicited events, or longer if deemed necessary by the investigator. Any unsolicited and solicited local (injection site) or systemic AEs, and vital signs (heart and respiratory rate, systolic and diastolic blood pressure [supine], and body temperature) will be documented by the study-site personnel following this observation period.
- i. Participants will be asked to note in the participant diary occurrences of injection site pain/tenderness, erythema, and swelling at the injection site daily. The extent (largest diameter) of any erythema and swelling should be measured using the supplied ruler and recorded daily. Body temperature (oral route preferred) should be measured at approximately the same time each day, preferably in the evening, using the supplied thermometer. If more than one measurement is made on any given day, the highest body temperature of that day will be used in the participant diary.
- j. AEs and special reporting situations related to study procedures or to noninvestigational sponsor products will be reported from the time a signed and dated ICF is obtained until the end of the study/early withdrawal. All other AEs (unsolicited) and other special reporting situations will be reported from the time of vaccination until 28 days after vaccination. All AEs leading to discontinuation of study vaccination (regardless of the causal relationship) are to be reported from the moment of vaccination until completion of the participant's last study-related procedure, which may include contact for safety follow-up.
- k. SAEs related to study procedures or to noninvestigational sponsor products will be reported from the time a signed and dated ICF is obtained until the end of the study/early withdrawal. All SAEs leading to discontinuation of study vaccination (regardless of the causal relationship) are to be reported from the moment of vaccination until completion of the participant's last study-related procedure, which may include contact for safety follow-up. All other SAEs (regardless of the causal relationship) are to be reported from the time of vaccination until the end of the study/early withdrawal.
- l. Concomitant therapies such as analgesic/antipyretic medications and nonsteroidal anti-inflammatory drugs, corticosteroids, and antihistaminic must be recorded until 28 days after vaccination. All other concomitant therapies should also be recorded if administered in conjunction with new or worsening AEs reported per protocol requirements outlined in Section 10.3, Appendix 3.
- m. Participants will be contacted at Day 8 to review the information noted in the participant diary. If the participant diary review is missed, the diary information will be reviewed during the following visit. The participant diary will be collected at the Day 15 visit.

1.3.2. Cohorts 2 and 3

Clinic Visit #	1	2	3	4	5 ^a	6	7	Early Exit ^b
Visit Timing		Vac	Vac + 7 d	Vac + 14 d	Vac + 28 d	Vac + 84 d (3 m)	Vac + 26 wk (6 m)	
Visit Day(s)	-28 to -1	1 ^c	8	15	29	85	183	
Visit Window			±2 d	-3 d/+7 d	±7 d	±14 d	±14 d	
Visit Type	Screening	STUDY VACCINATION	Safety	Safety and Immunogenicity	Safety	Safety and Immunogenicity	Safety and Immunogenicity	Early Exit
Written informed consent ^d	●							
Inclusion/exclusion criteria	●							
Demographics	●							
Medical history/prestudy therapy ^e	●	●						
Physical examination ^f	●	● 7	7	7	7	7	7	7
Vital signs ^g	●	2	●	●	●	●	●	●
Randomization	●							
Participant diary distribution	●							
Inclusion/exclusion criteria check ^h	●							
Contraindications to vaccination ⁱ	●							
Clinical safety laboratory blood sample, mL	● 10	1 5	● 5					3 5
Cellular immunity sample, mL		1 50		● 50		● 50	● 50	4 50
Humoral immunity sample, mL		1 10		● 10		● 10	● 10	4 10
Nasosorption sample		●		●		●	●	●
Vaccination		●						
30-minute postvaccination observation ^j		●						
Solicited AE recording ^k		-- Continuous --						5
Unsolicited AE recording ^l		----- Continuous -----						6
SAE recording ^m		----- Continuous -----						●
Concomitant therapy ⁿ		----- Continuous -----						●
Participant diary review of solicited AEs by study-site personnel			●					
Blood draw volumes								
Approximate daily blood draw, mL	10	65	5	60	-	60	60	65
Approximate cumulative study blood draw, mL	10	75	80	140	140	200	260	-

d = day; m = month; Vac = vaccination; wk = week.

● prevaccination; ● pre- and postvaccination; ● if the early exit visit is within 8 days after vaccination; ● blood samples for immunogenicity will only be taken if the early exit visit is at least 14 days after the previous immunogenicity blood draw; ● if the early exit visit is within 7 days after vaccination; ● if the early exit visit is within 28 days after vaccination; ● at the discretion of the investigator (based on health status of the participant).

- a. Can be electronic (eg, e-mail, text messages) or by phone.
- b. An early exit visit will be conducted for those participants who are unable to continue participation in the study and withdraw from the study before Day 183, but who do not withdraw consent. Participants who wish to withdraw consent from participation in the study will be offered an early exit visit (prior to formal withdrawal of consent).
- c. In addition, the first 4 participants in each cohort will be contacted by phone 24 hours after vaccination. In the absence of any clinical safety concerns, the remaining 8 participants of the cohort can be enrolled.
- d. Signing of the ICF should be done before any study-related activity.
- e. Prestudy therapies administered up to 30 days before vaccination must be recorded.
- f. A physical examination (including height and body weight) will be carried out at screening. At all other visits, an abbreviated, symptom-directed physical examination will be performed if deemed necessary by the investigator.
- g. Systolic and diastolic blood pressure (supine) and heart and respiratory rate measurements should be preceded by at least 5 minutes of rest in a quiet setting without distractions (eg, television, cell phones). Vital signs measurements should be taken before nasal sampling and blood draws, if applicable.
- h. To review inclusion criterion 3 and exclusion criteria 2, 8, 9, 10, 11, and 12.
- i. Investigator must check for acute illness or body temperature of $\geq 38.0^{\circ}\text{C}$ ($\geq 100.4^{\circ}\text{F}$) at the time of vaccination. In such cases, the participant may be vaccinated up to, and no later than, 10 days after the scheduled vaccination, or be withdrawn from vaccination at the discretion of the investigator.
- j. After vaccination, participants will be closely observed for a minimum of 30 minutes to monitor for the development of any acute reactions and solicited events, or longer if deemed necessary by the investigator. Any unsolicited and solicited local (injection site) or systemic AEs, and vital signs (heart and respiratory rate, systolic and diastolic blood pressure [supine], and body temperature) will be documented by the study-site personnel following this observation period.
- k. Participants will be asked to note in the participant diary occurrences of injection site pain/tenderness, erythema, and swelling at the injection site daily. The extent (largest diameter) of any erythema and swelling should be measured using the supplied ruler and recorded daily. Body temperature (oral route preferred) should be measured at approximately the same time each day, preferably in the evening, using the supplied thermometer. If more than one measurement is made on any given day, the highest body temperature of that day will be used in the participant diary.
- l. AEs and special reporting situations related to study procedures or to noninvestigational sponsor products will be reported from the time a signed and dated ICF is obtained until the end of the study/early withdrawal. All other AEs (unsolicited) and other special reporting situations will be reported from the time of vaccination until 28 days after vaccination. All AEs leading to discontinuation of study vaccination (regardless of the causal relationship) are to be reported from the moment of vaccination until completion of the participant's last study-related procedure, which may include contact for safety follow-up.
- m. SAEs related to study procedures or to noninvestigational sponsor products will be reported from the time a signed and dated ICF is obtained until the end of the study/early withdrawal. All SAEs leading to discontinuation of study vaccination (regardless of the causal relationship) are to be reported from the moment of vaccination until completion of the participant's last study-related procedure, which may include contact for safety follow-up. All other SAEs (regardless of the causal relationship) are to be reported from the time of vaccination until the end of the study/early withdrawal.
- n. Concomitant therapies such as analgesic/antipyretic medications and nonsteroidal anti-inflammatory drugs, corticosteroids, and antihistaminic must be recorded until 28 days after vaccination. All other concomitant therapies should also be recorded if administered in conjunction with new or worsening AEs reported per protocol requirements outlined in Section 10.3, Appendix 3.

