Initially, a sentinel group of 5 participants will be enrolled in Cohort 2 in a 2:2:1 ratio to Groups 6 to 8, respectively, before enrolling additional participants (Step 1). A blinded 24-hour postvaccination safety review will be performed by the principal investigator(s) (PI[s]) and sponsor team members (ie, at least the study responsible physician/study responsible scientist). In the absence of any clinical safety concerns, an additional 15 participants will be enrolled in a 2:2:1 ratio (Step 2). After review of the 7-day (Day 8) postvaccination safety data of these 20 participants by the DRC, the remaining participants in the cohort

will be randomized in a 2:2:1 ratio (Step 3). When all participants in Cohort 2 have completed the Day 8 postvaccination visit or discontinued earlier, all available safety data up to at least 7 days after vaccination of all participants in the cohort will be reviewed by the DRC. Based on this review, the sponsor may decide to not initiate enrollment of Cohort 3.

The enrollment of Cohort 3 will be conducted similarly to Cohort 2. Steps 1 and 2 will be performed with a sentinel group of 4 participants and with 12 participants, respectively, both enrolled in a 1:2:1 ratio. After review of the 7-day (Day 8) postvaccination safety data of these 16 participants by the DRC, the remaining participants in the cohort will be randomized in a 1:2:1 ratio.

After vaccination with study vaccine on Day 1, participants will remain under observation at the study site for a minimum of 30 minutes for presence of any acute reactions and solicited events, or longer if deemed necessary by the investigator. Any unsolicited and solicited local (injection site) or systemic AEs will be documented by the study-site personnel following this observation period. Each participant will record solicited local and systemic AEs and body temperature in the participant diary, beginning on the evening of the vaccination day and daily for 7 days after vaccination.

Nasosorption samples using synthetic absorptive matrix (SAM) strips, blood samples to assess humoral and cellular immune responses, and clinical safety laboratory blood samples (Cohorts 2 and 3 only) will be collected. Participant safety throughout the study will further be evaluated via physical examinations and vital signs.

NUMBER OF PARTICIPANTS

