 - After vaccination, participants will enter a 6-month safety and immunogenicity follow-up period. All AEs, serious adverse events (SAEs), and clinically significant laboratory abnormalities (including those persisting at the end of the study/early withdrawal) will be followed by the investigator until clinical resolution or until a clinically stable endpoint is reached, or until the participant has been deemed lost to follow-up after demonstration of due diligence of follow-up efforts. An early exit visit will be conducted for those participants who are unable to continue participation in the study and withdraw from the study before Day 183, but who do not withdraw consent. Participants who wish to withdraw consent from participation in the study will be offered an early exit visit (prior to formal withdrawal of consent) (Section 7.4).

- Several safety measures are included in this protocol to minimize the potential risk to participants, including the following:
 - An internal Data Review Committee (DRC) will be commissioned for this study (Section 9.6). In addition to the planned review of postvaccination safety data of participants in Cohorts 2 and 3, the DRC will be consulted if at least one of the study vaccination pausing rules has been met and/or if the participant's safety may be threatened.
 - There are prespecified rules that would result in pausing of further vaccination of participants if predefined conditions occur, preventing exposure of new participants to study vaccine until the DRC reviews all available safety data and subsequent communication between the sponsor and the PI(s) takes place (Section 7.3). When a first DRC meeting has been triggered by the occurrence of a given study vaccination pausing rule, the DRC will convene thereafter for each additional participant meeting that pausing rule. Possible actions upon review include, but are not limited to, study suspension, study adaptation, or discontinuation of further vaccination.
 - In Cohort 2, a sentinel group of 5 participants will be enrolled before enrolling additional participants (Step 1) (Section 4.1). In the absence of any clinical safety concerns upon a blinded 24-hour postvaccination safety review, an additional 15 participants will be enrolled (Step 2). After review of the 7-day (Day 8) postvaccination safety data of these 20 participants by the DRC, the remaining participants will be enrolled (Step 3).

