 - The enrollment of Cohort 3 will be conducted similarly to Cohort 2. Steps 1 and 2 will be performed with a sentinel group of 4 participants and with 12 participants, respectively, both enrolled in a 1:2:1 ratio. After review of the 7-day (Day 8) postvaccination safety data of these 16 participants by the DRC, the remaining participants in the cohort will be randomized in a 1:2:1 ratio.
 - Cohorts 2 and 3 will be enrolled in a staggered manner (Section 4.1). Based on the review of all available safety data up to at least 7 days after vaccination of all participants in Cohort 2 by the DRC, the sponsor may decide to not initiate enrollment of Cohort 3.
 - Contraindications to vaccination are included in Section 7.2.

Taking into account the measures taken to minimize risk to participants of this study, the potential risks identified in association with the Ad26/protein preF RSV vaccine are justified by the anticipated benefits that may be obtained.

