In the dose-up Cohort 2, a target of approximately 125 participants will be randomized in parallel in a 2:2:1 ratio to 3 groups (Table 2). Participants in Groups 6 and 8 will receive 1×10^{11} vp Ad26.RSV.preF/150 μ g RSV preF protein and placebo, respectively, while participants in Group 7 will receive 1.3×10^{11} vp Ad26.RSV.preF/150 μ g RSV preF protein.

In the dose-up Cohort 3, a target of approximately 100 participants will be randomized in parallel in a 1:2:1 ratio to 3 groups. Participants in Groups 9 and 11 will receive 1×10^{11} vp

Ad26.RSV.preF/150 µg RSV preF protein and placebo, respectively, while participants in Group 10 will receive 1.6×10^{11} vp Ad26.RSV.preF/150 µg RSV preF protein (Section 4.3).

Cohorts 1 and 2 may be enrolled in parallel, whereas Cohorts 2 and 3 will be enrolled in a staggered manner (Figure 1). A study site will not simultaneously enroll participants in more than one cohort. Cohort enrollment to each study site will be controlled via the interactive web response system (IWRS).

Initially, a sentinel group of 5 participants will be enrolled in Cohort 2 in a 2:2:1 ratio to Groups 6 to 8, respectively, before enrolling additional participants (Step 1). A blinded 24-hour postvaccination safety review will be performed by the PI(s) and sponsor team members (ie, at least the study responsible physician [SRP]/study responsible scientist [SRS]). In the absence of any clinical safety concerns, an additional 15 participants will be enrolled in a 2:2:1 ratio (Step 2). After review of the 7-day (Day 8) postvaccination safety data of these 20 participants by the DRC, the remaining participants in the cohort will be randomized in a 2:2:1 ratio (Step 3). When all participants in Cohort 2 have completed the Day 8 postvaccination visit or discontinued earlier, all available safety data up to at least 7 days after vaccination of all participants in the cohort will be reviewed by the DRC. Based on this review, the sponsor may decide to not initiate enrollment of Cohort 3.

The enrollment of Cohort 3 will be conducted similarly to Cohort 2. Steps 1 and 2 will be performed with a sentinel group of 4 participants and with 12 participants, respectively, both enrolled in a 1:2:1 ratio. After review of the 7-day (Day 8) postvaccination safety data of these 16 participants by the DRC, the remaining participants in the cohort will be randomized in a 1:2:1 ratio.

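### Footnote c of the Cohorts 2 and 3 schedule gives sentinel counts (4 phoned, then 8 enrolled) that conflict with the stepwise enrolment rule of 5 then 15 in Cohort 2 and 4 then 12 in Cohort 3

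*Protocol*

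**What the plan says.** Footnote c is attached to the Day 1 column of the Cohorts 2 and 3 schedule (Protocol 1.3.2) and states one rule for both cohorts: "the first 4 participants in each cohort will be contacted by phone 24 hours after vaccination". If no clinical safety concern arises, "the remaining 8 participants of the cohort can be enrolled".

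Section 4.1 sets a different rule for Cohort 2: "a sentinel group of 5 participants will be enrolled in Cohort 2 in a 2:2:1 ratio to Groups 6 to 8", then after the 24-hour review "an additional 15 participants will be enrolled in a 2:2:1 ratio (Step 2". The rest of the cohort waits for the DRC to review Day 8 data on those 20 participants. For Cohort 3, Section 4.1 gives 4 sentinels and then 12, with the same kind of DRC review at 16. The Synopsis (1.1) and the benefit-risk section (2.3.5) repeat these counts. The Schema (1.2) says that "a blinded 24-hour (Day 2) postvaccination safety review of the sentinel group of 5 participants will be performed" in Cohort 2. Section 9.6 ties the DRC reviews to the Day 8 visits of the 20th participant in Cohort 2 and the 16th in Cohort 3.

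The SAP (Section 3) refers to Section 4.1 of the protocol for the planned DRC reviews and gives no counts of its own.

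**The concern.** The schedule is what sites work from day to day. For Cohorts 2 and 3 it has no Day 2 column: after the Day 1 observation period, the next scheduled contact is Day 8 (±2 days), when the diary is reviewed. Footnote c is thus the only text that says how 24-hour safety information is to be collected, and it covers four people where the Cohort 2 review needs five.

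The release sentence fits neither cohort. It also speaks of the remaining participants of the cohort as released after the 24-hour call, whereas the protocol holds most of the cohort until the DRC has seen Day 8 data.

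At stake is how the first safety step is carried out for doses that Sections 4.2 and 4.3 describe as not previously given. A site relying on the footnote alone could omit a call and would have an unusable release number.

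**Working it through.** **Inputs.** Footnote c: 4, then 8. Section 4.1: Cohort 2 has 5 then 15 at 2:2:1, target 125; Cohort 3 has 4 then 12 at 1:2:1, target 100. Section 9.6: DRC review at 20 and 16. Table 2: Groups 6 to 8 are 50/50/25; Groups 9 to 11 are 25/50/25.

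**Step 1. Does the body text reproduce its own DRC counts?** Step 1 + Step 2: 5 + 15 = 20 and 4 + 12 = 16. Both match Section 9.6.

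**Step 2. Does it reproduce Table 2?** Step 3 is the target minus the DRC count: 125 − 20 = 105 and 100 − 16 = 84. Splitting each step by its ratio:

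| | Cohort 2 (Groups 6/7/8) | Cohort 3 (Groups 9/10/11) |
|---|---|---|
| Step 1 | 5 = 2/2/1 | 4 = 1/2/1 |
| Step 2 | 15 = 6/6/3 | 12 = 3/6/3 |
| Step 3 | 105 = 42/42/21 | 84 = 21/42/21 |
| Total | 125 = 50/50/25 | 100 = 25/50/25 |

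Every step is a whole number of allocation sets, and the totals equal Table 2.

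**Step 3. The same checks on the footnote.**

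- 4 + 8 = 12, which is neither 20 nor 16.
- After 4 participants, 125 − 4 = 121 remain in Cohort 2 and 100 − 4 = 96 in Cohort 3, not 8.
- At 2:2:1, 4 participants split as 1.6/1.6/0.8 and 8 as 3.2/3.2/1.6, so neither can be a whole allocation set in Cohort 2.
- At 1:2:1, 4 splits as 1/2/1 and agrees with the Cohort 3 sentinel group; 8 splits as 2/4/2 but conflicts with the stated 12.

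**Step 4. Count by count.**

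| | Footnote c | Body text | Agree? |
|---|---|---|---|
| Cohort 2, reviewed at 24 hours | 4 (phoned) | 5 | No |
| Cohort 2, enrolled next | 8 | 15 | No |
| Cohort 3, reviewed at 24 hours | 4 (phoned) | 4 | Yes |
| Cohort 3, enrolled next | 8 | 12 | No |

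**Step 5. Who is left out.** The five Cohort 2 sentinels comprise two at 1.3×10^11 vp, two at 1×10^11 vp and one on placebo. If every order within that set is equally likely (an assumption), the fifth is at the higher dose with probability 2/5 = 0.40. This describes who might be missed; it does not measure risk.

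**The case against.** The best reply is that this is a clerical slip with little consequence. The correct rule is stated consistently in several sections, and a footnote implying a cohort of 12 is so plainly wrong that a site would query it before acting on it. The 24-hour decision belongs jointly to the principal investigators and sponsor team members, so no site releases Step 2 alone. Randomization is central, and the interactive web response system controls cohort enrolment at each site. The body text does not require the 24-hour review to be by telephone, and the footnote does not forbid calling a fifth person. A visit-schedule footnote need not restate the DRC review.

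Much of this stands. The review of all five Cohort 2 sentinels is still required, the DRC reviews at 20 and 16 are unaffected, and the 30-minute observation, event recording, 24-hour reporting of serious events and pausing rules cover every participant. Read as a cap, 8 would expose fewer people. The missing DRC step is best seen as part of the same wrong sentence, not as a separate fault.

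It does not remove the point. The protocol nowhere says that the web response system enforces the enrolment steps. No other text supplies the 24-hour contact, so the required review of the fifth sentinel has no scheduled call behind it.

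**Conclusion.** The inconsistency is real, and the footnote is the text in error. Its counts are wrong in three of four places: 4 for 5 and 8 for 15 in Cohort 2, and 8 for 12 in Cohort 3. No other text reconciles them, and because the amendment history (Section 10.5) describes an original protocol, the footnote is current text.

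The practical size is one unscheduled 24-hour call in Cohort 2, plus a release number that sites in either cohort cannot use. The likely outcome is a missed call, a site query or a deviation. It should be fixed because it concerns the first safety check at a new dose, but it is not a design flaw. No added exposure is claimed, and no endpoint, sample size or analysis is affected. The counts rest only on the protocol's own figures and the planned targets of 125 and 100; only the 0.40 needs the equal-order assumption.

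**What to change.** Reword footnote c by cohort:

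- Cohort 2: phone participants 1 to 5 at 24 hours; if there is no clinical safety concern, enrol the next 15; enrol the last 105 or so only once the DRC has reviewed Day 8 data on the first 20.
- Cohort 3: phone participants 1 to 4 at 24 hours; if there is no clinical safety concern, enrol the next 12; enrol the last 84 or so only once the DRC has reviewed Day 8 data on the first 16.

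A shorter form would also do: all Step 1 participants are phoned at 24 hours, with a cross-reference to Section 4.1 for the enrolment steps. That leaves fewer places where counts can drift apart.

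The cost is one footnote, issued as a sponsor amendment under Appendix 4 (Section 10.4), and a notice to sites before the first Cohort 2 vaccination. The design, sample size and SAP stay as they are.
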